Note: if the clinical attending physician believes that bacterial pneumonia is likely and requires a second antibacterial agent for "atypical" infection (an uncommon occurrence in COVID-19), patients may receive another agent (e.g., doxycycline or levofloxacin) as appropriate at the clinician's discretion.

5.2.2. Azithromycin. Patients in the azithromycin arm will receive azithromycin 500mg on day 1 plus 250mg daily on days 2-5 (may be administered IV per clinician preference).

5.3 Study Assessments. Coordinators and/or data queries will classify the COVID Ordinal Outcomes Scale on days 1–7, 14. They will also review for adverse events, including especially rash, self-report of visual changes, or symptomatic hypoglycemia. They will ensure that an EKG is performed at 24 to 48 hours post-randomization time. If a clinical EKG is not performed during this timeframe, a research EKG will be performed. In addition, ventilator status and ICU and hospital stay (using the last-off method) will be used to determine ventilator- and ICU-free days at 28 days using the worst rank ordinal technique, whereby death is scored as -1 days. In addition, coordinators and/or data queries will classify the COVID Ordinal Outcomes Scale on day 14. If this cannot be determined from the medical record, the patient will be contacted via telephone, mail, or electronic methods to determine their status on day 14.

5.2.4 Six-month assessment. A brief visit will ascertain the EQ-5D-5L to measure quality of life. Mortality and readmissions will also be assessed at that visit, which may be performed by telephone, electronic means, or in-person, depending on the subject's needs and preferences.

5.4 Approach to potential risks. Hydroxychloroquine has been used in many thousands of patients as an anti-malarial agent and in systemic lupus erythematosus and rheumatoid arthritis as a mild anti-inflammatory agent. The safety has been well established. Azithromycin has been used in millions of patients and is effective against the causes of bacterial pneumonia. Its immunomodulatory effects are also of interest in a variety of syndromes. While both agents have known side effects, such side effects are generally rare and well-tolerated.

This pragmatic study protocol is designed to optimally protect patients against risk through careful choice of exclusion criteria, pragmatic monitoring for common adverse events, and careful oversight by a DSMB.

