General. Descriptive summaries will be produced for subject disposition, demographic and clinical characteristics of the randomized hydroxychloroquine and azithromycin groups. The primary analysis and other secondary analyses of efficacy outcomes will be performed in accordance with the intention-to-treat (ITT) principle, with all patients analyzed according to their randomized treatment assignment, irrespective of compliance. In addition to the formal statistical analyses described below, the proportions of subjects with each level of the 8-point COVID scale will be displayed in frequency tables and in graphical summaries for each day, from day 0 (baseline) through day 14 of follow-up. Other ordinal secondary outcomes will generally be summarized using medians, 10th, 25th, 75th, and 90th percentiles and plots of cumulative distribution functions. In cases where a substantial proportion of subjects fall into an extreme category, several of the indicated quantiles may take on the value of this category and a quantile-based summary may not be fully informative. In these cases, we will tabulate the proportions of subjects which fall into designated categories which are defined based on clinical relevance.

Adherence to the study medications will be summarized by providing the distributions of the proportion of doses of study medication which were administered to each patient overall and by randomized group. We will compute two proportions: 1) The proportion of protocol-intended dose, in which doses for which the patient had a protocol-specified reason not to receive study medication (e.g., prolonged QTc, died, or discharged home) will not be counted in the denominator for proportion of scheduled doses received. 2) The proportion of the total ideal dose, in which doses for which the patient had a protocol-specified reason not to receive study medication will be counted. We will also describe the median (IQR) for total doses received for both protocol-intended dose and ideal dose.

Analysis Sets. The primary analysis and analyses of secondary efficacy outcomes will be performed in the ITT population, which consists of all randomized patients. Although the trial was launched with the flexibility to enroll patients with suspected rather than confirmed COVID-19, no patients were HAHPS SAP

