Meier curves. Patients who die prior to day 28 are assigned an artificial follow-up time of 28 days censored at that point. This will assign to these patients a worse outcome than any surviving patients, and avoid conflating prolonged hospitalization with death. Descriptively, these time-to-event endpoints will be displayed as median (IQR). If fewer than half of patients meet the event before censoring, we will choose an appropriate quantile (e.g., first quartile) for description and display the proportions with events during the respective weeks of follow-up. For the sake of consistency, we will use the same ordinal regression model with the same prior distribution for the odds ratio as was used for the primary analysis to generate median posterior odds ratios and credible intervals for these endpoints.

Sub-groups. On a purely exploratory level, we will summarize effect variation in sub-groups defined by (a) age \geq 65 years, (b) symptom duration \geq 10 days, (c) in ICU at enrollment, (d) presence of at least one comorbidity, (e) race/ethnicity, and (f) receipt of any clinical azithromycin before enrollment. At early interim analyses, the sample size will be too small to support meaningful statistical inference, and we will limit presentation of results in sub-groups to descriptive summaries using the summary measures described for each outcome above.

Missing Data. We expect fewer than 5% of subjects will have missing data on either the primary or key secondary outcomes listed above. Hence, our primary analyses will be restricted to non-missing observations, without imputation. For the primary outcome, a sensitivity analysis will be performed by applying single imputation. Where daily COVID Ordinal Outcomes Scale scores are missing after hospital discharge, we will use last carried forward with the following modifications—patients discharged to a facility other than home will be classified as “home with limitations” (score 2), and patients found subsequently to be home with limitations will be rated as “home with limitations” from hospital discharge through that follow-up point. Patients who are discharged to home and found to have no limitations at day 14 will be rated as “home without” limitations starting at the time of hospital HAHPS SAP

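### The primary analysis is described as covering all randomized patients but uses only observed day-14 scores, and the missing scores should come mainly from discharged patients

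*SAP*

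**What the plan says.** SAP, Analysis Sets: the primary and secondary efficacy analyses "will be performed in the ITT population, which consists of all randomized patients".

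SAP, Missing Data: "We expect fewer than 5% of subjects will have missing data on either the primary or key secondary outcomes listed above", and for that reason "our primary analyses will be restricted to non-missing observations, without imputation". Protocol 5.7 pairs the same two statements.

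The SAP then adds a safeguard: "For the primary outcome, a sensitivity analysis will be performed by applying single imputation". Its rule is: "Where daily COVID Ordinal Outcomes Scale scores are missing after hospital discharge, we will use last carried forward with the following modifications". One modification is that "patients discharged to a facility other than home will be classified as" level 2. The other two modifications apply to patients later found to have limitations and to home discharges found free of limitations at day 14. Protocol 5.7 had planned multiple imputation for this sensitivity analysis, with earlier scale scores as auxiliary variables.

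On how the score is obtained, Protocol 5.3 uses the medical record first. Only if the record is insufficient, "the patient will be contacted via telephone, mail, or electronic methods to determine their status on day 14". The footnote to Protocol Appendix 1 has every patient scored on days 1 to 7 and 14, and patients still in hospital on day 14 scored on each of days 1 to 14.

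**The concern.** An analysis of observed scores is not an analysis of all randomized patients, and the only reason given for it is that few scores will be missing. A small amount of missing data is not necessarily ignorable. Levels 3 to 7 of the scale are hospital states and levels 1 and 2 are ambulatory states (Protocol 3.5, Table 1). Because the record supplies the hospital states, loss through failed contact falls mainly on the ambulatory end, so missingness depends on the outcome. The plan then sets aside what is known about these patients, namely their discharge status and earlier scores.

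The trial is open-label, so the chance of reaching a patient could differ by arm. If it did, one arm would lose more good outcomes than the other and the primary odds ratio would move. The question is by how much, and whether the planned sensitivity analysis would show it.

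**Working it through.** **Inputs.** From the documents: target N = 300; 95% follow-up, so 285 evaluable and 0.05 × 300 = 15 missing; the Scenario 2 and 3 control distributions; the prior for the log odds ratio, mean 0 and SD 0.354; the 95% posterior threshold. Assumed: 1:1 allocation, exactly 5% missing, all losses from levels 1–2 (the least favourable case), no covariates, and expected counts with 150 per arm. Because Scenario 3 has only 30.5% in levels 1–2, I also used an assumed distribution with 60% discharged (levels 1 to 8: 0.30, 0.30, 0.05, 0.12, 0.06, 0.04, 0.04, 0.09).

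**Step 1: the plan's own figure.** Whitehead's formula is N = 12(z_α + z_β)² / [(ln OR)² (1 − Σp̄³)], where p̄ is the mean of the two arms' level probabilities. With N = 285 it gives detectable odds ratios at 80% power of 0.560, 0.546 and 0.557 for Scenarios 1 to 3. SAP Table 4 has 0.56, 0.55 and 0.55, so it reproduces. With all 300 patients, Scenario 3 moves only from 0.557 to 0.565. Precision is not the issue.

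**Step 2: equal loss, 7.5 per arm.** Proportional-odds fits give 1.00 at the null. A true 0.55 becomes 0.53 in Scenarios 2 and 3, and 0.54 with 60% discharged.

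**Step 3: unequal loss, no true effect.** Take Scenario 3 and losses of 2% against 8%, that is 3 azithromycin and 12 hydroxychloroquine patients. Levels 1–2 start at 150 × 0.305 = 45.75 per arm and fall to 42.75 and 33.75; the other 104.25 per arm stay. The odds ratio for a score above 2 is then 42.75/33.75 = 1.27. For death (21.375 per arm, with 147 and 138 analyzed) it is (147 − 21.375)/(138 − 21.375) = 1.08. The common odds ratio lies between these:

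| Loss split | Scenario 3 | 60% discharged (assumed) |
|---|---|---|
| 2% vs 8% | 1.15 | 1.09 |
| 3% vs 7% | 1.10 | 1.06 |

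Reversing the arms moves the estimate the other way by about the same factor.

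The standard error of the log odds ratio is √[12/(285(1 − Σp̄³))]. With 1 − Σp̄³ about 0.97 in Scenario 3, this is 0.208, and ln(1.153)/0.208 = 0.68. For the 60% case the shift is 0.40 of a standard error.

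**Step 4: effect on the decision.** For the 1.15 case, the data precision is 1/0.208² = 23.1 and the prior precision is 1/0.354² = 7.98. The posterior mean is 0.142 × 23.1/31.1 = 0.106 and the SD is 1/√31.1 = 0.179, so Pr(OR > 1) = Φ(0.59) = 0.72, well short of 95%. Near the threshold it can matter. With a true odds ratio of 0.70 in Scenario 3, Pr(OR < 1) is 0.936 on full data. Losing 10 patients in one arm and 5 in the other makes it 0.895 if hydroxychloroquine loses more, or 0.970 if azithromycin does.

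**Step 5: does the sensitivity analysis repair it?** The two modifications for patients whose limitations are later established need a successful contact, and the third covers only discharge to a facility. A patient discharged home and never reached has the last score carried forward. The footnote to Protocol Table 1 scores each day by its worst status, so the score on the day of discharge is an inpatient one. Unless a post-discharge score exists, literal carry-forward gives level 3 or worse. For the Scenario 3 null case with 3 and 12 missing:

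- complete case: 1.15
- unreached patients placed at level 2: 1.01
- carried at level 3: 1.09
- carried at level 4: 1.15

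Carrying an inpatient score therefore repairs part of the shift or none of it, and agreement with the complete-case result could falsely reassure.

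**The case against.** A reader might infer that the dropped patients are already known to be level 1 or 2, and that patients are removed only from the best end of the scale. The documents do not support either. An unreached patient is known only to have left hospital. Protocol 5.2.4 plans to ascertain deaths and readmissions at six months, so neither is ruled out after discharge. Withdrawal can happen at any level, and consent to use data can be withdrawn too (Protocol 1.0 and 6.7). Imputation confined to levels 1–2 for every unreached patient would build the same assumption into the primary result.

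The restriction is also openly stated, capped by an expectation of under 5%, backed by several contact routes and retention measures (Protocol 5.3 and 5.5), and allowed for in the power table. Nothing in the documents suggests that contact will differ by arm: both arms receive active drug and neither continues it after discharge. If loss rates were equal, a split of 15 missing patients at least as extreme as 3 against 12 would arise by chance with probability 2 × (1 + 15 + 105 + 455)/2¹⁵ = 0.035. The sensitivity analysis helps where a post-discharge score exists, as it can for patients who left hospital within the first week.

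Finally, the carry-forward sentence might be a general scoring rule, which would leave few primary scores missing. Its place after the sensitivity-analysis sentence, and the SAP's later reference to similar single-imputation rules for sensitivity analyses, favour the narrower reading, but the text does not settle it.

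These points limit the size of the problem. They do not remove the mismatch between the stated set and the analyzed set, or the missing rule for unreached home discharges.

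**Conclusion.** The point stands in a limited form. The SAP names all randomized patients as the primary set and then analyzes only those with an observed day-14 score, and the missing scores should come mainly from discharged patients. The documents do not support the further inference that the primary result will be biased: material bias requires loss that differs by arm, which is an assumption here. Under the assumed 2% against 8% split the distortion is an odds ratio of about 1.09 to 1.15 at the null, enough to change the conclusion only when the posterior probability is already close to 95%. These figures are also at the unfavourable end, since they place every loss in levels 1–2. The more practical weakness is that the planned check may share the distortion. Severity: minor to moderate.

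**What to change.** - Make the primary analysis include every randomized patient, except where use of the data is refused. Multiply impute the missing day-14 score from discharge status and destination, baseline score, age and earlier daily scores.
- Restrict imputed values to levels 1–2 only where the record confirms that the patient was alive and out of hospital on day 14.
- Keep the complete-case analysis as a sensitivity analysis, described as randomized patients with an observed day-14 score.
- Replace the carrying forward of inpatient scores for home discharges never reached, and state whether the post-discharge rules govern primary scoring or only the sensitivity analysis.
- Report missingness by arm and by last known status.

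The cost is SAP wording, modest extra analysis work, and reliance on an imputation model for an expected share of under 5% of patients. The protocol already planned multiple imputation for this outcome, though as a sensitivity analysis and without restricting the imputed levels. If the sponsor prefers to keep the complete-case analysis as primary, the least that is needed is to stop calling it an analysis of all randomized patients and to define the missing rule.

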3.5 Primary endpoint

The WHO proposed (https://www.who.int/blueprint/priority-diseases/key-action/COVID-19_Treatment_Trial_Design_Master_Protocol_synopsis_Final_18022020.pdf) a slight modification of a preexisting COVID-19 ordinal endpoint, adding an extra status relevant only to prevention trials (no disease), and adding an extra status to reflect the difference between simple invasive ventilation and invasive ventilation plus additional organ support (ECMO, CRRT, or vasopressors). In the interest of synchronization, we will collect data to allow comparison with either the WHO or NIAID version of the scale. For analysis purposes, our primary endpoint is the WHO COVID Ordinal Outcomes Scale at day 14 (with the recognition that no patients are expected to have the status of never having developed a respiratory illness). The details of the endpoint are displayed in Table 1.

Table 1. WHO COVID Ordinal Outcomes Scale *		
Patient State	Descriptor	Score
Ambulatory	No limitation of activities	1
	Limitation of activities	2
Hospitalized, mild disease	No oxygen therapy	3
	Oxygen by mask or nasal cannulae	4
Hospitalized, severe disease	Non-invasive ventilation or high-flow oxygen	5
	Invasive mechanical ventilation without other organ support	6

	Invasive mechanical ventilation with other organ support (e.g., ECLS, CRRT, vasopressors)	7
Death	Dead	8

ECLS: extracorporeal life support; CRRT: continuous renal replacement therapy
*The score for the day reflects the worst status for the given calendar day

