5.4.5 Protection against loss of privacy. In order to protect a potential subject's privacy, we will take multiple steps to protect the study subject from breach of confidentiality. The list linking the subject's name and medical record number will be kept behind the hospital firewall in a password-protected file. This file will only be accessible through the hospital server to those individuals given password approval to access the file. Furthermore, the electronic database (REDCap) will be coded with a unique study identifier rather than with individually identifiable PHI (other than certain dates of service, as indicated above).

5.5 Cohort retention techniques. Study follow-up will incorporate published, validated techniques for maximizing cohort retention.²⁰⁻²³ These retention techniques include careful logging of contact attempts, confirmation of contact information at each encounter, multi-modality contact approaches (e.g., letters, emails, phone calls, social media, spontaneous home visits) as necessary. We anticipate minimal difficulty with cohort retention.

5.6 Data collection. Research coordinators and/or investigators will collect data and record them on paper and/or electronic CRFs. Data quality will be reviewed using front-end range and logic checks at the time of data entry and back-end monitoring of data using electronic reports. Patient records and case report forms will be examined locally (including, as appropriate, duplicate data entry) on a random basis to evaluate the accuracy of the data entered into the database and monitor for protocol compliance with expanded quality assurance efforts if the non-congruence rates exceed 5%. The coordinating center will maintain these data according to relevant regulations and security standards within a REDCap database. Note that given concerns for contagion during the pandemic, coordinators will practice “no-touch” practices for data collection and entry.

5.7 Analysis and interpretation of data. A formal statistical analysis plan (SAP) will be written and finalized before the conclusion of enrollment and before the beginning of data analysis. The principles of this SAP are outlined here.

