Appendix 1. Visit schedule

Procedure	Visit						
	Baseline	24-48 hours post-randomization	Daily through 5 days	14 days	Hospital discharge	28 days	6 months
Screening procedures	X						
Informed consent and LAR identification	X						
Patient reconsent (where necessary)					X		
Data collection	X				X		
EKG (research or clinical)		X					
Study drug			X				
Active Adverse Event review			X				
Passive Adverse Event review					X		
WHO ordinal scale				X*			
VFD, ICUFD, HFD						X	
EQ-5D-5L							X

LAR: legally authorized representative; WHO: World Health Organization; VFD: Ventilator-free days; ICUFD: ICU-free days; HFD: hospital-free days; EQ-5D-5L: EuroQol-5 dimensions-5 level

*measured daily, days 1–7, 14 on all patients; measured days 1–14 on patients still hospitalized on day 14.

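### As written, the SAP's single-imputation rule for day 14 gives an in-hospital score to a patient sent home who has no post-discharge score

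*SAP*

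**What the plan says.** The primary analysis uses observed day-14 scores only. The SAP (Missing Data) adds one sensitivity analysis for that outcome, by single imputation. Its default is: "Where daily COVID Ordinal Outcomes Scale scores are missing after hospital discharge, we will use last carried forward with the following modifications". Three modifications follow:

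- Facility: "patients discharged to a facility other than home will be classified as" limited at home, score 2. No later contact is needed.
- Home, limited: "patients found subsequently to be home with limitations will be rated as" score 2 from discharge through that follow-up.
- Home, not limited: "Patients who are discharged to home and found to have no limitations at day 14 will be rated as" without limitations, score 1, from discharge.

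Three places in the protocol bear on which score would be the last one:

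- Table 1 (section 3.5) gives 1 and 2 to ambulatory patients, 3 to 7 to hospitalized patients and 8 to death. Its footnote reads: "The score for the day reflects the worst status for the given calendar day".
- The Appendix 1 footnote has the scale "measured daily, days 1–7, 14 on all patients; measured days 1–14 on patients still hospitalized on day 14".
- Section 5.3 looks for day-14 status in the medical record first: "If this cannot be determined from the medical record, the patient will be contacted via telephone, mail, or electronic methods to determine their status". Section 5.5 adds "multi-modality contact approaches", including home visits.

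**The concern.** The two exceptions for patients at home both depend on the patient's status being found later. A patient sent home whose day-14 status cannot be established from the record or by contact meets neither, and is not a facility discharge. Only the default is left. If no score was taken after discharge, the score carried forward is an in-hospital one.

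The day-14 value is then a category that the scale defines as being in hospital, for someone last known to have left it. The ordering is also odd: an unreached home discharge scores 3 or more, while a facility discharge scores 2. At stake is the usefulness of the only missing-data check that the SAP itself states for the primary outcome. A check that puts these patients in a category their discharge contradicts says little about whether dropping them matters.

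**Working it through.** **Tracing the rule.** The plan states no figure for this rule, so the check is of the text, case by case.

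| Patient with day-14 score missing or filled back | Rule that applies | Day-14 score |
|---|---|---|
| Sent to a facility | Facility modification | 2 |
| Sent home, later found limited | Home, limited | 2 |
| Sent home, found unlimited at day 14 | Home, not limited | 1 |
| Sent home, no post-discharge score, never reached | Default | Last in-hospital score, 3 or more |

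The last row most plausibly arises for discharge after day 7. Appendix 1 schedules days 8 to 13 only for patients still in hospital on day 14. Discharge on day 7 itself gives the same result, because that day's score takes the worst status. A patient on mask or nasal oxygen on day 7 would be imputed 4.

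**Reach.** The SAP expects fewer than 5% missing: 0.05 × 300 = 15, so fewer than 15 patients for all reasons. The documents do not say how many would be unreached home discharges. I assume 5, a third of that ceiling, and show wider cases.

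**Effect on the odds ratio (OR).** Assumptions: 150 per arm; day-14 distributions from the SAP's Scenarios 2 and 3; missing patients truly at level 1 or 2, drawn in proportion; carried score 3 or 4 (a higher one would shift more). I fitted an unadjusted proportional-odds model to the expected counts. Splits are azithromycin / hydroxychloroquine; cells are Scenario 2 / Scenario 3; the true OR is 1.

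| Split | Complete case | Carry 3 | Carry 4 | Fill 2 | Fill 1 |
|---|---|---|---|---|---|
| 2.5 / 2.5 | 1.000 / 1.000 | 1.000 / 1.000 | 1.000 / 1.000 | 1.000 / 1.000 | 1.000 / 1.000 |
| 2 / 3 | 1.014 / 1.015 | 1.011 / 1.009 | 1.020 / 1.016 | 1.000 / 1.001 | 0.992 / 0.995 |
| 1 / 4 | 1.043 / 1.045 | 1.034 / 1.028 | 1.060 / 1.048 | 1.000 / 1.004 | 0.977 / 0.985 |
| 0 / 5 | 1.073 / 1.077 | 1.057 / 1.047 | 1.102 / 1.082 | 1.000 / 1.006 | 0.962 / 0.975 |

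At a true OR of 0.75 with split 2 / 3, carry-forward and complete case both give about 0.76.

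**Scale of the shift.** V = (n/12)(1 − Σp³) and SE = 1/√V. For Scenario 2, Σp³ = 0.067, V = 25 × 0.933 = 23.3 and SE = 0.207. For Scenario 3, SE = 0.203. The largest 2 / 3 shift is ln(1.020)/0.207, about 0.1 SE.

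With the SAP prior (SD 0.354), the shrinkage factor is 0.354²/(0.354² + 0.207²) = 0.745 and the posterior SD is 0.179. For carry 4, the posterior OR is exp(0.745 × ln 1.020) = 1.015. A P1 that would have been 0.950 (z = 1.645) becomes Φ(1.645 − 0.745 × ln 1.020/0.179) = 0.941. Across both scenarios and both carried scores it is 0.941 to 0.946. The matching complete-case value is about 0.943 to 0.944.

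**An extreme case.** If all 15 missing patients were of this type and split 3 / 12, carry-forward gives 1.09 to 1.19 and complete case about 1.15. With equal loss, a split at least that uneven has two-sided probability 0.035 (binomial, 15 trials, p = 0.5).

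**The case against.** **Intent.** All three modifications end in an ambulatory category, and the reason given for them concerns only whether limitations persist after discharge. The authors may well have meant to carry forward an ambulatory status. That is a fair reading of the purpose. But the SAP names no score, 1 or 2, for an unreached home discharge, and the default it does name produces 3 or more when no post-discharge score exists.

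**The window.** Discharge after day 7 is inferred from Appendix 1. SAP General promises daily displays through day 14, and protocol section 5.3 allows scoring by data query and from the record. If ambulatory scores were collected on days 8 to 13, the pattern would be rarer. If scores on days 1 to 7 were not obtained after discharge, it could also reach earlier discharges. This stands: the window is plausible, not established.

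**No harm shown.** At a true OR of 1, carrying a 3 lies closer to 1 than complete case in every unequal split above. Carrying a 4 is worse in Scenario 2 and close to complete case in Scenario 3. That is correct. However, under these assumptions both carried scores move the same way as the complete-case error, so agreement between the two analyses could reassure without cause.

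**Another check exists.** Protocol section 5.7 specifies multiple imputation, and the SAP does not expressly withdraw it. The statement that single imputation is the only check therefore holds for the SAP alone.

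**Stronger readings to avoid.** A reader might infer that the trial's main result is biased, or that one arm is favored. The documents support neither. The primary analysis does not impute, and nothing suggests that loss differs by arm.

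**Conclusion.** The point holds as a literal reading of the SAP and is minor. The stated default gives a patient discharged home with no post-discharge score a day-14 value that Table 1 reserves for inpatients, and ranks that patient worse than a facility discharge. That is an incorrect value from a stated rule, so it goes beyond a missing detail. It does not show that the authors intended to code discharged patients as hospitalized.

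At a true OR of 1 the shift is nil with equal loss. It is about 1.01 to 1.02 for a 2 / 3 split of five patients, and 1.05 to 1.10 only if all five fall in the hydroxychloroquine arm. The count of five, the splits and the true levels of 1 or 2 are assumptions. Because those levels are assumed, the good performance of filling with 1 or 2 is partly built in. The case for the fix rests on the definition of the scale. Only the sensitivity analysis is affected.

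**What to change.** Add to SAP Missing Data: no in-hospital score is carried past discharge. For patients discharged home with no known readmission or death by day 14 and no day-14 status, impute 2 and repeat with 1. The two runs bracket the result over the ambulatory scores; they do not cover an unrecorded readmission or death.

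Add one table of missing day-14 scores by arm and discharge destination, so that a reader can see how many patients the rule touches and whether loss was balanced.

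The cost is a sentence or two in the SAP and one table. No new data are needed and the complete-case primary analysis stays as it is.
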